| Calcitonin, CEA (≥18 years of age) | | X | | | X | See Instructions | X | | X | | Perform on Day 1 of Cycles 2-16. After completion of 1 year of treatment, obtain every 12 weeks in adult patients (Cycles 16, 19, 22, etc.). |
| Calcitonin, CEA (<18 years of age) | | X | | | X | X | X | | X | | Calcitonin, CEA will be performed on adolescent patients every 4 weeks starting on Day 1 of Cycle 2-n and throughout. |
| Serum Cortisol, ACTH | | X | | | X | See instructions | | | X | | Only in patients with Cushing’s disease related to their cancer. Baseline, C1D15, then q 8 weeks (±7 days) for the first 24 weeks after C1D1 and q 12 weeks (±7 days) thereafter (i.e., at the same time as imaging assessments). |
| Phone visit (collection of | | | | | | See Instructions | | | | | Applicable only for adult patients. |

| Screening, On-Study, and Post-Study Treatment Follow-Up Schedule of Activities for Patients on Arm A and Arm B | | | | | | | | | | | |
|--|------------------------|----|------------------|-----|-----------|---------------------------------------|------------------|-----------------------------------|----------------------------------|--|---|
| | Screening | | On-Treatment | | | Safety assessments prior to crossover | | Post-Study Treatment | | | Instructions |
| | | | Cycle = 28 days | | | (only for patients on Arm B) | | | | | |
| | (Day Relative to C1D1) | | Cycle 1 | | Cycle 2-n | V201 ^a | | Short-term follow-up ^a | Long term Follow-up ^b | | |
| | | | (±3 days) | | (±3 days) | Day 1-30 (±7 days) | 1-x days | (30 ± 7 days) | (90 ± 14 days) | | |
| ≤42 | ≤7 | D1 | D8 | D15 | D1 | N/A | N/A | V801 | V802-8XX | | |
| Procedure | | | | | | | | | | | |
| concomitant medications, AEs, labs, and patient dosing diary) | | | | | | | | | | | Onsite clinical visit will occur every 28 days from C2 to C16. After C16 the onsite visit will occur every 12 weeks (i.e., C19, C22, C25, etc.). A phone follow-up visit will occur at every non-clinical visit after C16 (i.e., C17, C18, C20, C21, C23, C24, etc.) where details related to concomitant medications, AEs, chemistries, pregnancy test (if required), and patient dosing diary will be captured. |
| Growth plate imaging | X | | See instructions | | | | | | | | Only for patients <18 years of age who have not reached full adult height. Knee MRI at baseline and every 6 months ±2 weeks). See Section 8.2. |

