| Radiologic imaging (neck, chest, abdomen, pelvis and other known sites of disease) | X (28 days) | | See instructions | | | | See instructions | X | | | 
 Perform according to RECIST 1.1 criteria, by the same method used at baseline, q 8 weeks (±7 days) for the first 24 weeks after C1D1 and q 12 weeks (±7 days) thereafter until radiographic disease progression or death, whichever occurs first. If the imaging submitted to confirm progression by BICR was performed more than 28 days prior to dosing, new imaging should be completed as the pre-dosing |

| Screening, On-Study, and Post-Study Treatment Follow-Up Schedule of Activities for Patients on Arm A and Arm B | | | | | | | | | | | |
|--|------------------------|----|------------------|-----|-----------|---------------------------------------|----------|-----------------------------------|----------------------------------|------------------|---|
| Procedure | Screening | | On-Treatment | | | Safety assessments prior to crossover | | Post-Study Treatment | | | Instructions |
| | | | Cycle = 28 days | | | (only for patients on Arm B) | | | | | |
| | (Day Relative to C1D1) | | Cycle 1 | | Cycle 2-n | V201 ^a | | Short-term follow-up ^a | Long term Follow-up ^b | | |
| | | | (±3 days) | | (±3 days) | Day 1-30 (±7 days) | 1-x days | (30 ± 7 days) | (90 ± 14 days) | | |
| ≤42 | ≤7 | D1 | D8 | D15 | D1 | N/A | N/A | V801 | V802-8XX | | |
| | | | | | | | | | | | baseline (but does not need reconfirmed by BICR). • See Section 8.1 for details, including information on suggested modalities. |
| Submit scans | X | | See instructions | | | | X | | X | | All scans taken for tumor assessment should be submitted to Lilly’s designee preferably within 5 business days of collection for central review by the BICR. Repeated submission of scans greater than 10 business days after date of collection will be considered a protocol deviation (unless previously approved by sponsor). |
| Survival and PFS2 assessment | | | | | | | | | X | See instructions | Perform q 3 months (±7 days) for the first year off treatment, q 4 months (±14 days) for the second year off treatment, then approximately every 6 months thereafter. Will last until the final analysis for OS. If an in-person visit is not possible, confirm survival by contacting the patient directly via phone. See Section 8.1.1 regarding PFS2 assessment. |
| Collection of poststudy-treatment | | | | | | | | | X | X | |

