- ^b Long-term follow-up begins when the patient completes the 30-day (± 7 days) follow-up visit and ends with the patient's death, upon loss to follow-up, or upon overall study completion, whichever is earlier. No follow-up procedures will be performed for a patient who withdraws informed consent unless he or she has explicitly provided permission and consent.

Note: Baseline/screening assessments and laboratory values drawn within the indicated window of C1D1 may be used for both screening/baseline and C1D1 assessments. There is not a defined interval required from randomization to C1D1.

1.3.3. Exceptional Control Arm Switch Treatment (for participants switching from vandetanib to cabozantinib)

This SoA table reflects the additional or revised procedures for control arm switch. Refer to the SoA table, Section 1.3.2 for complete schedule.

| Exceptional^a Control Arm Switch Treatment (for participants switching from vandetanib to cabozantinib) | | | | | | |
|--|--|-----------------|-----|----|------------------|---|
| | Switch Screening | On-Treatment | | | | |
| | | Cycle = 28 days | | | | |
| | Days relative to start of switch treatment | Cycle X+1 | | | Cycle X+2 – 3 | Instructions |
| | | (±3 days) | | | (±3 days) | |
| ≤42 | D1 | D8 | D15 | D1 | | |
| Procedure | | | | | | |
| Eligibility criteria for control arm switch | X | | | | | See Section 6.1.3.1. Must be confirmed before any switch phase procedures are performed. |
| Informed consent form | X | | | | | ICF must be signed before any switch phase procedures are performed. |
| Vital signs (≥18 years of age) | X | X | X | | See Instructions | Measure vital signs: Perform on Day 1 of Cycles X+2 - X+3: weight, systolic and diastolic blood pressure, pulse rate, and body temperature. After the first 3 cycles of switch treatment, go back to previous frequency, i.e., completion of 1 year of study treatment, obtain every 12 weeks in adult participants only. |
| Vital signs (<18 years of age) | X | X | X | | See instructions | Vital signs will be performed on adolescent participants every 4 weeks starting on Day 1 of Cycle X+2-n and throughout. Height should be measured every 6 months. |
| ECG | X | X | X | | See Instructions | Obtain triplicate local ECGs at screening, on D1 and D8 of Cycle X+1, on Day 1 of Cycles X+2 - X+3. After 3 cycles of switch treatment, go back to previous frequency. It is preferable to obtain ECGs approximately 2 hours after dosing. See Section 8.2.1. |

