8.1. Efficacy Assessments

8.1.1. Imaging

Efficacy assessments include tumor evaluation every 8 weeks after treatment initiation through week 24, and then every 12 weeks thereafter as noted in the SoA. Images are to be submitted for BICR evaluation within 5 days of completion. Patients who discontinue treatment without radiographic progression by BICR should continue to be assessed per the above schedule until radiographic disease progression is confirmed by BICR or death.

All patients are required to undergo neck, chest, abdomen, and pelvis imaging at baseline and subsequent serial imaging at disease assessment time points. All images will be collected at a central facility for central reviewer assessment during the study. Response will be assessed per RECIST 1.1 requirements (Eisenhauer et al., 2009).

Finally, all patients will enter Long-Term Follow-Up (LTFU) for confirming disease progression (if not occurring on treatment), subsequent anticancer therapy(ies), and survival.

Baseline disease assessment with radiographic tumor measurements using computed tomography (CT) or magnetic resonance imaging (MRI) of neck, chest, abdomen, and pelvis or any other areas with suspected disease involvement must be completed within 28 days of C1D1. MRI with contrast is the preferred imaging modality for imaging the abdomen and pelvis of subjects with

MTC given the inherent challenges in RECIST 1.1 assessment of MTC liver metastases. If MRI is not obtainable, triple phase CT of the abdomen (nonenhanced, arterial phase, and portal venous phase imaging) with pelvis is recommended. Routine single-phase CT of the abdomen and pelvis in the portal venous phase if the recommendations listed above are not obtainable. Brain imaging is required at baseline only for patients with a history of CNS metastases, or if clinically indicated and subsequent serial scans are required if brain metastases are present at baseline (MRI preferred, CT with contrast is acceptable if MRI contraindicated). Bone imaging is required at baseline only for patients with known bone metastases or if clinically indicated, and subsequent serial scans are required if bone metastases are present at baseline (MRI or CT with bone windows preferred).

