8.1.1. Definitions

Definitions of efficacy, safety, and patient-reported outcome (PRO) analysis variables are listed in respective sections of the SAP. Other variables are listed below alphabetically:

- Age (years): $(\text{informed consent date} - \text{date of birth} + 1)/365.25$; birth month and day are imputed to be 01 July, because only the birth year is collected through electronic case report form (eCRF).
- Baseline Measurement: unless otherwise specified, the last nonmissing measurement prior to the first dose of study drug for safety and tolerability analyses, and the last nonmissing measurement prior to randomization for baseline and efficacy analyses.
- Crossover Baseline Measurement: unless otherwise specified, the last nonmissing measurement prior to the first dose of selpercatinib during crossover period for safety, tolerability, and efficacy analyses.
- Duration: duration is calculated as:
 - Duration (days): $(\text{end date} - \text{start date} + 1)$
 - Duration (weeks): $(\text{end date} - \text{start date} + 1)/7$
 - Duration (months): $(\text{end date} - \text{start date} + 1)/30.4375$
(days in months = $(1/12) * \text{average number of days in a year}$)
 - Duration (years): $(\text{end date} - \text{start date} + 1)/365.25$
- Duration of disease: $(\text{randomization date} - \text{diagnosis of cancer date} + 1)$.
- Study Day (safety and tolerability analyses): study day is calculated as assessment date – first dose date + 1 day if the assessment is done on or after the first dose day. If the assessment is done prior to the first dose day, the study day will be calculated as assessment date – first dose date. Date of first dose is defined as Study Day 1.

- Study Day (baseline and efficacy analyses): study day is calculated as assessment date – randomization date + 1 day if the assessment is done on or after randomization. If the assessment is done prior to randomization, the study day will be calculated as the assessment date – randomization date. Date of randomization is defined as Study Day 1.
- Time-to-Event: the event or censoring time (days) is calculated as the date of event/censoring – randomization date + 1.

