$$Z_{PFS,CHW} = \sqrt{\frac{e_{PFS,1}}{e_{PFS,2}}} Z_{PFS,1} + \sqrt{\frac{e_{PFS,2} - e_{PFS,1}}{e_{PFS,2}}} \left\{ \frac{\sqrt{e_{PFS,2}^*} Z_{PFS,2} - \sqrt{e_{PFS,1}} Z_{PFS,1}}{\sqrt{e_{PFS,2}^* - e_{PFS,1}}} \right\}$$

As pointed out by Cui, Hung, and Wang (Cui et al. 1999), for group sequential test based on the repeated significance test that can be asymptotically expressed as a Brownian motion process, eg logrank test, with independent increment property, if the conventional logrank statistic is replaced by the CHW statistic while using the original rejection boundary for the conventional logrank statistic, the new CHW test will have the total type I error preserved at the specified level. Therefore, to determine the statistical significance at the final analysis, the $Z_{PFS,CHW}$ will be compared to the Z scale critical boundary -1.960 given in Section 8.8 Interim Analysis.

In addition, unadjusted HR between treatment arms will be estimated using a stratified Cox regression model (Cox 1972), stratified by randomization strata. Progression free survival curves, medians, and PFS rates at various time points with 95% CI for each treatment arm will be estimated using the Kaplan-Meier method (Kaplan and Meier 1958).

Table JZJB.3 defines censoring rules to be applied to the BICR PFS main analysis.

Table JZJB.3. PFS Censoring Scheme

Situation	Event/Censor	Date of Event or Censor
Tumor progression ^a by BICR or death	Event	Earliest date of PD by BICR or death
No tumor progression by BICR and no death	Censored	Date of last adequate tumor assessment ^b , per RECIST 1.1 criteria, or date of randomization (whichever is later)
No baseline radiologic tumor assessment available	Unless	
No adequate postbaseline tumor assessment available	Censored	Date of randomization
and death reported after 2 scan intervals ^c following randomization	Censored	Date of randomization
New systemic anticancer therapy	Censored	Date of adequate tumor assessment, per RECIST 1.1 criteria, prior to start of new therapy or date of randomization (whichever is later)
Tumor progression by BICR or death documented immediately after 2 or more missing scan intervals following last adequate tumor assessment or randomization (whichever is later)	Censored	Date of last adequate tumor assessment, per RECIST 1.1 criteria, or date of randomization (whichever is later)

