8.5. Tertiary/Exploratory Endpoint Analyses

Calcitonin response rate

Calcitonin response rate is defined as percentage of patients who had a decline from baseline in the calcitonin level of at least 50% maintained for at least 4 weeks. Calcitonin response rate will be compared between Arm A and Arm B using a CMH test stratified by the randomization strata.

CEA response rate

Carcinoembryonic antigen (CEA) response rate is defined as percentage of patients who had a decline from baseline in the CEA level of at least 50% maintained for at least 4 weeks.

Carcinoembryonic antigen response rate will be compared between Arm A and Arm B using a CMH test stratified by the randomization strata.

PROs

Further details of planned analysis of PROs will be provided in a separate SAP.

PFS/ORR/DOR/DCR After Crossover

Progression-free survival after crossover in crossover population is defined as the time from start of selpercatinib treatment until the occurrence of disease progression or death from any cause. Patients known to be alive and without disease progression will be censored at the time of the last adequate tumor assessment.

Duration of response is defined as the time from the date that measurement criteria for CR or PR with respect to the crossover baseline tumor assessment are first met until the first date that disease is recurrent or documented disease progression is observed, or the date of death from any cause in the absence of documented disease progression or recurrence during crossover period.

Survival curve, the median, and rates at various time points with 95% CI will be estimated using the Kaplan-Meier method (Kaplan and Meier 1958).

Overall response rate after crossover is defined as the number of patients who achieve a BOR of CR or PR with respect to the crossover baseline tumor assessment, divided by the total number of patients in crossover population. Disease control rate after crossover is defined as the number of patients who achieve a BOR of CR, PR or stable disease (SD) lasting 16 or more weeks, with respect to the crossover baseline tumor assessment, divided by the total number of patients in crossover population. The ORR and DCR after crossover with 95% CI will be summarized.

Additional exploratory analyses to compare efficacy endpoints prior versus post crossover intra-patient may be performed as deemed appropriate.

TEAE and Lab Abnormalities After Crossover

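### The SAP takes core-period efficacy baseline from before randomization, but the protocol times the calcitonin/CEA sample and any repeat baseline scan to first dose, so a valid untreated value can be set aside

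*Protocol*

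**What the plan says.** **Protocol, anchored to C1D1.**

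- The Schedule of Activities in 1.3.2 counts screening days relative to C1D1. Its closing note lets values taken inside the C1D1 window serve as baseline, then adds: "There is not a defined interval required from randomization to C1D1".
- Protocol 6.1 gives a soft limit: treatment should start within 7 days of randomization.
- In 1.3.2, the only pre-treatment mark for calcitonin and CEA is in the column for 7 days or fewer before C1D1.
- Protocol 8.1.1 says that baseline imaging "must be completed within 28 days of C1D1". The imaging row in 1.3.2 adds that if the scan sent to confirm progression was done "more than 28 days prior to dosing, new imaging should be completed as the pre-dosing" baseline, and that this repeat scan needs no new central confirmation.

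**SAP, anchored to randomization.** Section 8.1.1 gives three rules, with the usual proviso that another baseline may be specified elsewhere:

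- Safety and tolerability use the last value before first dose.
- Core-period efficacy uses "the last nonmissing measurement prior to randomization for baseline and efficacy analyses".
- The crossover period uses "the last nonmissing measurement prior to the first dose of selpercatinib during crossover period for safety, tolerability, and efficacy analyses".

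SAP 8.5 defines calcitonin response as a "decline from baseline in the calcitonin level of at least 50% maintained for at least 4 weeks", and CEA response in the same way. SAP 8.4.2 defines maximum change in tumor size, shown in a waterfall plot from investigator assessments, as a ratio to baseline. Neither section names a different baseline.

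**The concern.** The two documents count from different days. A sample or scan that the protocol accepts as baseline can be dated after randomization, and the SAP rule then does not recognize it.

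For calcitonin and CEA no earlier sample is scheduled, so the patient has no SAP baseline and a 50% decline cannot be derived. For tumor size, the SAP baseline becomes the older eligibility scan in place of the scan that the protocol ordered because the older one was out of date. In both cases an untreated value nearer to first dose has been collected and is set aside by a stated rule. SAP 8.1.1 already uses first dose as the anchor for safety, tolerability and crossover efficacy, so core-period efficacy is the exception within the same section.

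**Working it through.** The plan states no figure on this point, so there is nothing to reproduce. The check is date arithmetic in whole days.

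**Inputs**

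- g = days from randomization to C1D1: 0 to 7 (Protocol 6.1, worded as a recommendation).
- d = days from the calcitonin/CEA sample to C1D1: 0 to 7 (Protocol 1.3.2).
- Imaging window: 28 days before C1D1 (Protocol 8.1.1).
- a = age in days of the eligibility scan at randomization.

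**Calcitonin and CEA.** The sample falls between randomization and first dose when d < g.

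- At g = 0 this cannot happen.
- At g = 7 it happens for every d from 0 to 6; at d = 7 the sample falls on the day of randomization.
- Example: g = 7 and d = 3. The sample is drawn 7 − 3 = 4 days after randomization and 3 days before any drug. It meets both protocol timing rules. No scheduled sample precedes randomization, so the SAP baseline is missing.
- Across patients the share without an SAP baseline runs from 0% (all sampled before randomization) to 100% (all sampled after it, for example before the dose on C1D1). The documents give neither the gaps nor the sampling days.

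**Scans.** A repeat baseline scan is called for when a + g > 28.

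- At g = 7 this means a > 21. A scan aged 22 to 28 days is still in its window at randomization but out of it at dosing, so the need for a repeat may only become clear after randomization.
- Example: a = 25 and g = 7. The eligibility scan is 25 + 7 = 32 days old at dosing. A repeat 3 days before C1D1 is dated 4 days after randomization. The protocol baseline is the 3-day-old scan; the SAP baseline for tumor-size change is the 32-day-old scan.
- At g = 7, the last 7 of the 28 permitted days lie after randomization: 7/28 = 25% of the window. This is a share of calendar days, not of patients.

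**The case against.** The strongest reply is that these items come before randomization anyway. Protocol 8 requires all screening evaluations to be completed and reviewed to confirm eligibility. Protocol 4.1 randomizes after eligibility is confirmed. The 7-day column sits under the screening header, and Protocol 8.1.1 describes baseline imaging as obtained in the screening period. On that reading the number affected is zero. This stands as a statement of what is likely. It does not amount to a requirement: calcitonin and CEA are not eligibility criteria in 5.1 or 5.2, and the repeat scan is triggered by the dosing date and needs no reconfirmation, so no eligibility step holds either one before randomization.

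Second, SAP 8.1.1 allows another baseline to be specified, and the protocol itself names the repeat scan as the pre-dosing baseline. That carries weight for how scans are read. It does nothing for calcitonin and CEA, and the SAP states no exception for tumor-size change.

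Third, SAP 8.1.2 says that analyses use observed data and that missing data are not imputed unless specified. This indicates how a missing baseline would be treated, but not why a collected value should count as missing.

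Fourth, a baseline fixed before allocation is a defensible choice in an open-label trial. This stands for investigator-read scans, some of which would be read after the arm is known. For calcitonin and CEA, which Protocol Appendix 2 assigns to the central laboratory, the risk is negligible.

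A reader might also infer from the 1.3.2 note that the gap is unlimited. Protocol 6.1 does not support that, although the two statements should be reconciled.

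**Conclusion.** The mismatch is real and minor. It affects the exploratory calcitonin and CEA response rates and the descriptive tumor-size plot, and only for patients whose sample or repeat scan falls between randomization and first dose. Their number is unknown. A reader might put it at a sizeable fraction of the trial, but any single figure needs assumed distributions of gaps and sampling days that the documents do not contain.

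A reader might also infer harm to the primary endpoint: if the eligibility scan were the baseline, the repeat scan could be read as progression before any dose, pulling the hazard ratio toward 1 and costing power. The documents do not support this. A PFS event is a progression call by blinded central readers under RECIST 1.1, or death (Protocol 9.4.3.1, SAP 8.3.2). SAP 8.1.1 does not tell those readers which scan to compare with, and the protocol calls the repeat scan the baseline. The BICR Charter, which is not among the documents, may settle the matter. The censoring row in Table JZJB.3 for "No baseline radiologic tumor assessment available" should rarely if ever be triggered by this mismatch, because progression must be confirmed on imaging before randomization. PFS, TFFS and OS are timed from randomization whichever baseline is used. No effect on PFS, its hazard ratio or power is shown.

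**What to change.** In SAP 8.1.1, for calcitonin, CEA and tumor measurements, define core-period baseline as the last assessment on or before first dose, and for patients never dosed as the last on or before randomization. Report by arm how many of these baselines are dated after randomization; this also shows how far the open-label risk for investigator-read scans reaches. In the note under Protocol 1.3.2, say that the windows count back from C1D1 and refer to Section 6.1 for the start of treatment.

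The cost is one SAP definition, one count by arm and one cross-reference. No new data are needed, and the definition then has the same anchor as the SAP's safety and crossover baselines.
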